7.3 Interim Analysis

To identify any possible safety issues, two blinded reviews of reported SAEs, AEs including AEs of special interest, injection site reactions and laboratory safety data were performed after:

- The first 150 participants across all sites had received their 1st vaccination and the 14 days safety follow-up data were available
- The first 150 participants across all sites had received their 2nd vaccination and the 14 days safety follow-up data were available

No comparison of treatment arms was done during the blinded safety reviews and therefore an adjustment of the α -level is not relevant.

In protocol amendment 3, a partial unblinding using dummy IDs was introduced to allow analysis of WB ICS data. The trial team will remain blinded. Please see the protocol section 7.6.2. for details. As for the other exploratory endpoints, no adjustment for multiplicity will be made.

8 Data handling and programming rules

8.1 Handling of Missing Values

For the primary efficacy endpoint missing values will be handled using censoring. The primary endpoint is analysed based on the mITT which includes all randomised participants except those with TB disease recurrence before Visit 6, Day 70 (or 14 days after 2nd dose for those who received both vaccinations). Participants without TB disease recurrence confirmed by of *Mtb* by culture of sputum samples are censored. Asymptomatic participants not capable of producing sputum will be censored as well.

No imputation of missing values will be performed.

8.2 Partial and missing dates

Partial TB diagnosis and TB treatment start dates will be handled as follows: If day is missing, the day will be set to the 1st of the month. If the month is missing the month will be set to January. If the year is missing the date will be set to missing.

Partial TB treatment end dates will be handled as follows: If day is missing, day will be set to the last day of the month. If the month is missing, the month will be set to six months after the start month.

Partial dates of general concomitant medication and medical history will not be imputed.

Partial AE start dates will be handled as follows: If day is missing then day will be set to the first day of the month unless a vaccination occur in the same month. In that case day will be set to the day of vaccination. If month is missing the month will be set to the first month of the year unless at least one vaccination occurs that year. In that case the month will be set to the month of the first vaccination of the year. If the AE start date is missing the date will be set to the date of the first vaccination.

Partial AE end dates will be handled as follows: If the day is missing, the day will be set to the last day of the month. If month is missing, month will be set to the last month of the year. If the AE end date is missing the AE will be considered ongoing at end of trial and the date will not be imputed.

8.3 Other derivations

Duration of AEs

Duration of an AE in days will be calculated as:

$$\text{Date}_{\text{AE end}} - \text{Date}_{\text{AE start}} + 1$$

The calculation will be based on AE dates after handling of partial dates. Duration will not be calculated for ongoing AEs.

Time to event

Time to event (or censoring) in days will be calculated as

$$\text{Date}_{\text{end-timepoint}} - \text{Date}_{\text{start-timepoint}} + 1$$

9 Deviations from protocol

The following deviations in the statistical analyses compared to the protocol are made:

- The protocol section 6.1 states that the per-protocol [PP] analysis set will consist of all participants who received both doses of H56:IC31 or placebo within the specified dose intervals, who entered the evaluation period for efficacy 14 days after receipt of the second dose of H56:IC31 or placebo with no HIV seroconversion, and who had no major protocol deviations (to be defined in the statistical analysis plan). Regarding major protocol deviations, the definition is updated to *who had no major protocol deviation of clinical or statistical significance*.
- The protocol section 7.3.1 states that supportive robustness and consistency analysis will be performed using the PP and ITT populations for the primary endpoint. Since
 - the only difference between the mITT and the ITT population is that the mITT will include all randomised participants except those with TB disease recurrence before Visit 6, Day 70
 - the primary endpoint only include TBs diagnosed by confirmation of *Mtb* by culture of sputum, during the period starting 14 days after the 2nd vaccination (Day 70, Visit 6) then are the mITT and ITT analyses exactly identical, why the ITT analyses of the primary endpoint from day 70 will be replaced by analyses from day 0.
- The protocol section 7.3.1 states that summaries of median time to initial diagnosis of TB disease recurrence will be presented by treatment group and trial site. Due to the expected low number of recurrent TB diseases, it will not be possible to estimate the median time to initial diagnosis and this is therefore not included in the SAP. The endpoint contains censored events and a non-parametric summary of time to TB disease recurrence is not appropriate.

10 Software

All statistical calculations described in this SAP will be done by using SAS, release 9.4 or later (SAS Institute, Cary, NC, USA).

Who drug dictionary version September 2018 will be used for coding of prior and concomitant medication.

MedDRA version 21.1 will be used for coding of medical history and AEs.

Appendix A: Immunogenicity SAP

Appendix A contains the final immunogenicity SAP by [REDACTED] and [REDACTED] dated 04 September 2023.

H56:IC31 vaccine immunogenicity statistical analysis plan

1. Background: This statistical analytical plan (SAP) will outline the approaches to be undertaken to analyse data for the immunogenicity endpoint in the H56:IC31 A055 trial. The key objective is to quantify and characterize immunological responses to H56:IC31 vaccination in TB patients who have completed antibiotic therapy. The first 100 participants from [REDACTED] and [REDACTED] will be included in the immunogenicity cohort. The first 50 participants randomized at the [REDACTED] clinical site and the first 50 randomized at the [REDACTED] site will be included such that approximately half of the participants from each site would have received the vaccine and another half the placebo. Immunogenicity samples will be collected at baseline (Day 0) and 14 days after the second vaccination (Day 70), and then processed to measure antigen-specific immune responses.

Table 1: Summary of immunogenicity evaluation

Sample type	Assay	Immunogenicity endpoint	Approximate blood volume	Study days	Study site
Whole blood	WB ICS	Secondary endpoint (Primary immunogenicity endpoint)	6 ml	0, 70	[REDACTED] [REDACTED]

2. Objectives:

2.1. Primary objective:

2.1.1. To determine if H56:IC31 vaccination boosts antigen-specific Th1 and Th17 T cell responses.

2.1.1.1. We will measure frequencies (background subtracted) of recombinant H56 protein-specific CD4 T-cells expressing any combination of IL-2, IFN- γ , TNF, and/or IL-17 (i.e. the total cytokine response) at Day 0 and Day 70 in each study arm.

Statistical method(s):

1. Wilcoxon signed-rank test will be used to compare responses between Day 0 and Day 70 within each study arm. A p-value < 0.05 will be considered significant.
2. Mann-Whitney test will be used to compare the baseline-corrected response (Day 70 responses minus the Day 0 responses) between the two study arms. The effect size and 95% CI will be reported and a p-value < 0.05 will be considered significant.

Mann-Whitney test will be used to compare responses across study arms at Day 70. The effect size and 95% CI will be reported and a p-value < 0.05 will be considered significant.

2.2. Secondary objective(s):

2.2.1. To determine which cytokine co-expressing T cell subsets are boosted by H56:IC31 vaccination.

2.2.1.1. We will quantify frequencies (background subtracted) of recombinant H56 protein-specific CD4 T-cell subsets that co-express combinations of IL-2, IFN- γ , TNF, and/or IL-17 at

Day 0 and Day 70 in each study arm, and determine which of these subsets predominate the vaccine-boosted response. We will focus on the following 3 T cell subsets as primary outcomes based on prior experience with H56:IC31 vaccination in human trials:

1. CD4 T-cells co-expressing IL-2 and TNF
2. CD4 T-cells co-expressing IL-2, IFN- γ , and TNF
3. CD8 T-cells expressing any combination of IL-2, IFN- γ , TNF, and/or IL-17 (total response)

We will therefore address the following objectives:

2.2.1.2. Compare frequencies (background subtracted) of recombinant H56 protein-specific CD4 T-cells co-expressing IL-2 and TNF (double positives) between Day 0 and Day 70 in each study arm, and at Day 70 across study arms.

2.2.1.3. Compare frequencies (background subtracted) of recombinant H56 protein-specific CD4 T-cells co-expressing IL-2, IFN- γ , and TNF (triple positives) between Day 0 and Day 70 in each study arm, and at Day 70 across study arms.

2.2.1.4. Compare frequencies of recombinant H56 protein-specific CD8 T-cells expressing any combination of IL-2, IFN- γ , TNF, and/or IL-17 between Day 0 and Day 70 in each study arm, and at Day 70 across study arms.

Statistical method(s):

1. Wilcoxon signed-rank test will be used to compare responses between Day 0 and Day 70 within each study arm.
2. Mann-Whitney test will be used to compare the baseline-corrected response (Day 70 responses minus the Day 0 responses) between the two study arms. The effect size and 95% CI will be reported and a p-value < 0.05 will be considered significant.
3. Mann-Whitney test will be used to compare responses across study arms at Day 70. The effect size and 95% CI will be reported and a p-value < 0.05 will be considered significant.

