6.4.1 Antigen specific cell mediated immune responses by WB ICS

Antigen specific cell mediated immune responses by WB ICS at baseline (Visit 3, Day 0), and 14 days after the 2nd vaccination (Visit 6, Day 70) is a secondary endpoint and the primary immunogenicity endpoint. For assessment of the immunogenicity of H56:IC31 by WB ICS, only whole blood samples from the immunogenicity cohort are included (See sections 1 and 2.2).

Responses will be measured by flow cytometry (up to 15 parameters) with the WB ICS assay. The variables of interest for assessment of antigen-specific cell-mediated immune response to vaccination will be the percentage of CD4⁺ and CD8⁺ T-cells that express the cytokines IL-2, IFN- γ , TNF- α , and IL-17 in the following combinations:

- H56 protein-specific CD4⁺ T-cells expressing the total cytokine response, i.e., any combination of IL-2, IFN- γ , TNF- α , and/or IL-17
- H56 protein-specific CD4⁺ T-cells co-expressing IL-2 and TNF- α
- H56 protein-specific CD4⁺ T-cells co-expressing IL-2, IFN- γ , and TNF- α
- H56 protein-specific CD8⁺ T-cells expressing any combination of IL-2, IFN-g, TNF- α , and/or IL-17 (total response)

The percentages of T-cell responses will be presented in summary tables and box plots including median, quartiles and range by treatment and visit including change from Visit 3 to Visit 6.

The immunogenicity analysis set will also be used for analysis of antigen specific cell mediated immune responses by WB ICS, please see Appendix A.

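### The primary immunogenicity objective covers Th1 and Th17 responses, but no compared outcome isolates IL-17, so the Th17 half cannot be answered as planned

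*SAP*

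**What the plan says.** Whole-blood ICS is a secondary endpoint of the trial and its primary immunogenicity endpoint (Protocol 7.4.1, SAP 6.4.1). The hypothesis-testing plan for it is in SAP Appendix A.

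- **Objective (2.1.1):** "To determine if H56:IC31 vaccination boosts antigen-specific Th1 and Th17 T cell responses".
- **Measure (2.1.1.1):** background-subtracted frequency of H56-specific CD4 T cells positive for one or more of four cytokines (IL-2, IFN-γ, TNF, IL-17). The appendix calls this the total cytokine response, measured on Days 0 and 70 in each arm.
- **Tests:** a signed-rank test within arm, a Mann-Whitney test at Day 70, and the baseline-corrected comparison: "Mann-Whitney test will be used to compare the baseline-corrected response (Day 70 responses minus the Day 0 responses) between the two study arms". Each is judged at p < 0.05 on that total.
- **Secondary objective (2.2.1.1):** CD4 subsets that co-express combinations of the four cytokines will be quantified at "Day 0 and Day 70 in each study arm, and determine which of these subsets predominate the vaccine-boosted response". The plan then narrows: "We will focus on the following 3 T cell subsets as primary outcomes based on prior experience with H56:IC31 vaccination in human trials". These are IL-2/TNF CD4 cells, IL-2/IFN-γ/TNF CD4 cells and the CD8 total.
- **Main SAP (6.4.1):** the same four outcomes, the first being CD4 cells "expressing the total cytokine response, i.e., any combination of" the four cytokines.

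**The concern.** The objective names two responses, and the measure returns one number in which they are merged. A cell counts the same whether it makes IFN-γ only or IL-17 only. If the total is significant, the one criterion attached to the objective has been met, yet nothing in it shows that IL-17 moved. If Th17 rises and Th1 does not, a small IL-17 fraction can be swamped by variation in the Th1 fraction.

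What is at stake is the wording of the main immunogenicity conclusion. The scientists who analyse these data hold a list linking dummy IDs to treatment before the trial is unblinded (Protocol 7.6.2). With no IL-17 outcome fixed in advance, any IL-17 subset stressed later would be open to the charge of selection.

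**Working it through.** **1. Where does IL-17 enter?** The documents state no power, sample-size reasoning or effect size for this objective, so there is no planned figure to reproduce. The check is on definitions.

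| Compared outcome | Cell type | Role of IL-17 |
|---|---|---|
| Total response (2.1.1.1) | CD4 | pooled with three others |
| IL-2/TNF double positives (2.2.1.2) | CD4 | not used |
| IL-2/IFN-γ/TNF triple positives (2.2.1.3) | CD4 | not used |
| Total response (2.2.1.4) | CD8 | pooled, and not a T-helper readout |

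Two pool IL-17, two do not use it, and 0 of 4 isolate it. Table shells 14.2.5.1 to 14.2.5.8 (two per outcome) and the columns of Listing 16.2.6.6 carry the same four outcomes. The comparisons in 2.2.1.2 and 2.2.1.3 read "CD4 T-cells co-expressing IL-2 and TNF (double positives) between Day 0 and Day 70 in each study arm, and at Day 70 across study arms" and "and TNF (triple positives) between Day 0 and Day 70 in each study arm, and at Day 70 across study arms".

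**2. Can the total be separated afterwards?** Split it into H (cells with at least one of IL-2, IFN-γ and TNF, with or without IL-17) and S (cells with IL-17 only). Then total = H + S. One observed change cannot identify two unknowns, and any rise is compatible with no change in S. A Th1 cell that also starts to make IL-17 stays in H and leaves the total unchanged.

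**3. Dilution.** Let s be the share of S in the baseline total, and f_H and f_S the fold changes. Fold change of the total = (1 − s)·f_H + s·f_S. The documents do not give s; 5%, 10% and 20% are assumed.

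| Scenario | s = 5% | s = 10% | s = 20% |
|---|---|---|---|
| Th1 × 1.8, IL-17 unchanged | 1.71 + 0.05 = 1.76 | 1.62 + 0.10 = 1.72 | 1.44 + 0.20 = 1.64 |
| Th1 × 1.8, IL-17 halved | 1.71 + 0.025 = 1.735 | 1.62 + 0.05 = 1.67 | 1.44 + 0.10 = 1.54 |
| Th1 unchanged, IL-17 × 2 | 0.95 + 0.10 = 1.05 | 0.90 + 0.20 = 1.10 | 0.80 + 0.40 = 1.20 |

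**4. Illustrative rejection rates.** These use 50 per arm (the planned cohort), log-normal responses, and the baseline-corrected Mann-Whitney test at two-sided 0.05. All SDs, shares and fold changes are assumptions.

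*Set A* (SD of ln baseline 0.9, SD of ln change 0.6, 3000 trials; s = 5%, 10%, 20%):
- Th1 × 1.8, IL-17 unchanged: total significant in 99%, 99%, 97%.
- Th1 × 1.8, IL-17 halved: 98%, 95%, 81%.
- IL-17 × 2, Th1 unchanged: 9%, 21%, 49%. A separate IL-17 outcome detects this in over 99%.

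*Set B* (log-SD 0.8, Day 0/Day 70 correlation 0.6, 2000 trials; s = 5%, 20%):
- Th1 × 1.5 only: 76%, 71%. Th1 × 2 only: 99.8%, 99.3%. A separate IL-17 outcome is significant in 4% to 6%, about the nominal level.
- IL-17 × 2 only: 8%, 37%. A separate IL-17 outcome: 99.8% at both shares.

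*Sensitivity.* At s = 10%, smaller Th1 rises make the total significant less often: 26% at 1.2-fold, 47% at 1.3-fold, 82% at 1.5-fold. At s = 5%, detection by a separate IL-17 outcome falls to 85% or 72% if its SD of ln change is 1.0 or 1.2. It falls to 85% or 53% if measurement noise has an SD equal to, or twice, the median IL-17 level.

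**The case against.** A reader might infer that a Th1-only boost will be reported as a Th1 and Th17 boost. The documents do not support that. No rule converts a significant total into a Th17 statement, the outcome is labelled a total, and the table titles name all four cytokines. Th1 and Th17 may also be loose wording for the cytokine panel.

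Item 2.2.1.1 is a planned step towards attributing the pooled result: it will describe which co-expressing CD4 subsets dominate, and these may include IL-17. That stands, and it narrows the gap without closing it. The named comparisons leave those subsets out, and co-expression does not clearly cover IL-17 single positives.

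The missing IL-17 table is weak evidence on its own, because the ICS shells show only N, median, quartiles and range, and carry none of the Appendix A tests. The argument therefore rests on the outcome definitions.

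The weight is also limited. The protocol and main SAP objective is simply antigen-specific cell-mediated responses; Th1 and Th17 appear only in Appendix A. SAP 6.6 plans no formal analysis of the other secondary endpoints, and SAP 7.3 groups this analysis with the exploratory ones. Yet Appendix A calls the objective primary and attaches tests and a significance level to it, so it should have a matching measure.

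Finally, the simulated rates are not trial evidence, and the gain from a separate outcome shrinks if IL-17 frequencies lie near assay background. That is conceded.

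**Conclusion.** The mismatch is real and can be checked from the text alone: the objective has two parts, and none of the four compared outcomes can confirm or refute the second. A significant total could be over-read as a Th17 boost, and a Th17-only effect could be missed. It would go too far to say that misreporting will happen, or that IL-17 is ignored altogether.

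The size cannot be fixed from the documents. Under the assumptions shown, a Th1-only rise of about two-fold makes the total significant in 97% or more of trials, and a Th17-only doubling does so in 8% to 49%. Smaller Th1 effects or noisier IL-17 data change these rates; the definitional gap does not depend on them. The point is worth correcting because it is cheap. It concerns a secondary immunogenicity objective and does not touch the primary efficacy analysis.

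**What to change.** In Appendix A 2.1.1.1 and SAP 6.4.1, add two separate outcomes:

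- (a) CD4 T cells expressing any IL-17;
- (b) CD4 T cells expressing IL-2, IFN-γ and/or TNF.

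State how cells positive for both IL-17 and a Th1 cytokine are handled. Give each outcome the same baseline-corrected between-arm comparison with effect size and 95% CI, and keep the total as a summary. Base any Th17 statement on (a) alone, and require both (a) and (b) for a joint claim. Add the matching tables (2 outcomes × analysis set and cohort = 4) and listing columns. If treatment-linked whole-blood ICS data have already been analysed, label the added outcomes post hoc.

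The simpler alternative is to reword 2.1.1 to the total CD4 cytokine response and make no Th17 claim.

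The first option costs a few more tables and tests from the planned four-cytokine flow data, with no new samples. The second costs one line of text and gives up the Th17 question.

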Appendix B: AESI

AESI as specified in the protocol, Appendix A:

Adverse events of special interest represent a subset of AEs that include autoimmune diseases and other systemic disorders of interest which could potentially have an autoimmune etiology. Adverse events of special interest are listed below. The PI should use clinical and scientific judgment in deciding whether other adverse events (i.e., events not listed here) could have an autoimmune origin.

- Acute disseminated encephalomyelitis (ADEM)
- Addison's Disease
- Anti-neutrophil Cytoplasmic Antibody (ANCA)-associated Vasculitis
- Ankylosing Spondylitis
- Anti-phospholipid Syndrome
- Autoimmune Bullous Skin Diseases
- Autoimmune Hemolytic Anemia
- Autoimmune Hepatitis
- Basedow's Disease
- Behcet's Syndrome
- Bell's Palsy
- Carditis
- Celiac Disease
- Crohn's Disease
- Cutaneous Lupus
- Demyelinating Disease
- Dermatomyositis
- Diabetes Mellitus, Insulin Dependent (IDDM)
- Erythema Nodosum
- Glomerulonephritis
- Guillain Barre Syndrome
- Grave's Disease
- Idiopathic Thrombocytopenic Purpura (ITP)
- Inflammatory Bowel Disease (non-specific)
- Juvenile Rheumatoid Arthritis
- Mixed Connective Tissue Disease
- Multiple Sclerosis
- Myasthenia Gravis
- Myelitis/Transverse Myelitis
- Myocarditis
- Nephritis
- Optic neuritis
- Pericarditis

Appendix C: Steroids and anti-inflammatory drugs

Steroids and anti-inflammatory drugs of interest are defined as the below ATC level 4 codes.

ATC Code	ATC text
A07EC	AMINOSALICYLIC ACID AND SIMILAR AGENTS
C05AA	CORTICOSTEROIDS
H02AA	MINERALOCORTICIDS
H02AB	GLUCOCORTICIDS
H02BX	CORTICOSTEROIDS FOR SYSTEMIC USE, COMBINATIONS
J04AA	AMINOSALICYLIC ACID AND DERIVATIVES
L04AA	SELECTIVE IMMUNOSUPPRESSANTS
L04AB	TUMOR NECROSIS FACTOR ALPHA (TNF-) INHIBITORS
L04AC	INTERLEUKIN INHIBITORS
L04AD	CALCINEURIN INHIBITORS
L04AX	OTHER IMMUNOSUPPRESSANTS
M01AA	BUTYLPYRAZOLIDINES
M01AB	ACETIC ACID DERIVATIVES AND RELATED SUBSTANCES
M01AC	OXICAMS
M01AE	PROPIONIC ACID DERIVATIVES
M01AG	FENAMATES
M01AH	COXIBS
M01AX	OTHER ANTIINFLAMMATORY AND ANTIRHEUMATIC AGENTS, NON-STEROIDS
M01BA	ANTIINFLAMMATORY/ANTIRHEUMATIC AGENTS IN COMBINATION WITH CORTICOSTEROIDS
M01BX	OTHER ANTIINFLAMMATORY/ANTIRHEUMATIC AGENTS IN COMBINATION WITH OTHER DRUGS
M01CA	QUINOLINES
M01CB	GOLD PREPARATIONS
M01CC	PENICILLAMINE AND SIMILAR AGENTS
M01CX	OTHER SPECIFIC ANTIRHEUMATIC AGENTS
N02BA	SALICYLIC ACID AND DERIVATIVES
N02CB	CORTICOSTEROID DERIVATIVES
V10AX	OTHER ANTIINFLAMMATORY THERAPEUTIC RADIOPHARMACEUTICALS

Appendix D: Prohibited medication

Prohibited medication is defined as the below ATC codes:

Category	ATC code	ATC Text
Immune response affecting treatments. Prohibited from 42 days before visit 3 until and including visit 6 (Day 70).	A14AA	ANDROSTAN DERIVATIVES
	A14AB	ESTREN DERIVATIVES
	B02BB	FIBRINOGEN
	B02BC	LOCAL HEMOSTATICS
	B02BD	BLOOD COAGULATION FACTORS
	B02BW	HERBAL CONTAINING VITAMIN-K
	B02BX	OTHER SYSTEMIC HEMOSTATICS
	B05AA	BLOOD SUBSTITUTES AND PLASMA PROTEIN FRACTIONS
	B05AX	OTHER BLOOD PRODUCTS
	B06AA	ENZYMES
	B06AB	OTHER HEM PRODUCTS
	B06AC	DRUGS USED IN HEREDITARY ANGIOEDEMA
	B06AW	HERBAL DECOAGULANT
	C05AA	CORTICOSTEROIDS
	H01AA	ACTH
	H01AB	THYROTROPIN
	H01AC	SOMATROPIN AND SOMATROPIN AGONISTS
	H01AX	OTHER ANTERIOR PITUITARY LOBE HORMONES AND ANALOGUES
	H01BA	VASOPRESSIN AND ANALOGUES
	H01BB	OXYTOCIN AND ANALOGUES
	H01CA	GONADOTROPIN-RELEASING HORMONES
	H01CB	SOMATOSTATIN AND ANALOGUES
	H01CC	ANTI-GONADOTROPIN-RELEASING HORMONES
	H02AA	MINERALOCORTICOIDS
	H02AB	GLUCOCORTICOIDS
	H02BX	CORTICOSTEROIDS FOR SYSTEMIC USE, COMBINATIONS
	H02CA	ANTICORTICOSTEROIDS
	J06AA	IMMUNE SERA
	J06BA	IMMUNOGLOBULINS, NORMAL HUMAN
	J06BB	SPECIFIC IMMUNOGLOBULINS
	J06BC	OTHER IMMUNOGLOBULINS
	L03AA	COLONY STIMULATING FACTORS
	L03AB	INTERFERONS
	L03AC	INTERLEUKINS
	L03AW	HERBAL IMMUNOMODULATORS
	L03AX	OTHER IMMUNOSTIMULANTS
	L04AA	SELECTIVE IMMUNOSUPPRESSANTS

	L04AB	TUMOR NECROSIS FACTOR ALPHA (TNF-) INHIBITORS
	L04AC	INTERLEUKIN INHIBITORS
	L04AD	CALCINEURIN INHIBITORS
	L04AX	OTHER IMMUNOSUPPRESSANTS
	M01BA	ANTIINFLAMMATORY/ANTIRHEUMATIC AGENTS IN COMBINATION WITH CORTICOSTEROIDS
	N02CB	CORTICOSTEROID DERIVATIVES
	V07AC	BLOOD TRANSFUSION, AUXILIARY PRODUCTS
Licensed vaccines. Prohibited from visit 1 until and including visit 6 (Day 70) except for SARS-Cov-2 vaccines recommended by national vaccination programs if administered more than 28 days before or after IMP	J07AC	ANTHRAX VACCINES
	J07AD	BRUCELLOSIS VACCINES
	J07AE	CHOLERA VACCINES
	J07AF	DIPHTHERIA VACCINES
	J07AG	HEMOPHILUS INFLUENZAE B VACCINES
	J07AH	MENINGOCOCCAL VACCINES
	J07AJ	PERTUSSIS VACCINES
	J07AK	PLAGUE VACCINES
	J07AL	PNEUMOCOCCAL VACCINES
	J07AM	TETANUS VACCINES
	J07AN	TUBERCULOSIS VACCINES
	J07AP	TYPHOID VACCINES
	J07AR	TYPHUS (EXANTHEMATICUS) VACCINES
	J07AX	OTHER BACTERIAL VACCINES
	J07BA	ENCEPHALITIS VACCINES
	J07BB	INFLUENZA VACCINES
	J07BC	HEPATITIS VACCINES
	J07BD	MEASLES VACCINES
	J07BE	MUMPS VACCINES
	J07BF	POLIOMYELITIS VACCINES
	J07BG	RABIES VACCINES
	J07BH	ROTA VIRUS DIARRHEA VACCINES
	J07BJ	RUBELLA VACCINES
	J07BK	VARICELLA ZOSTER VACCINES
	J07BL	YELLOW FEVER VACCINES
	J07BM	PAPILLOMAVIRUS VACCINES
J07BX	OTHER VIRAL VACCINES	
J07CA	BACTERIAL AND VIRAL VACCINES, COMBINED	
Investigational treatment. Prohibited from visit 1 until and including visit 8 (Day 421)	V98	INVESTIGATIONAL DRUG

